Principal-Investigator:

Dr. med. dent. [name]

Signature

Clinical Study Protocol - Clinical evaluation of a new dual cure universal adhesive (Adhese Universal DC) in the indirect restorative therapy: A randomised, controlled clinical trial

(ClinO, Appendix 3, 1.1, 2.1, 3.1, 4.1; Appendix 5, 2b)

Sponsor / Sponsor-Investigator	Ivoclar Vivadent AG
Study Title:	Clinical evaluation of a new dual cure universal adhesive (Adhese Universal DC) in the indirect restorative therapy: A randomised, controlled clinical trial
Short Title / Study ID:	Clinical evaluation of Adhese Universal DC in the indirect restorative therapy / LL3615088
Protocol Version and Date:	03 10.03.2021
Trial registration:	Registry of the U.S. National Library of Medicine (http://www.clinicaltrials.gov): NCT04475679. Supplementary federal database (Portal for clinical trials in Switzerland - SNCTP, https://www.kofam.ch/en/snctp-portal/): SNCTP000004028. As soon as the new electronic system EUDAMED is operational, the clinical investigation will be retrospectively registered.
Study category and Rationale	Category A According to Article 20 Categorisation of clinical trials of medical devices this clinical trial is a category A clinical trial since a medical device that has conformity marking will be used and the medical device will be used according to its instruction for use.
Clinical Phase:	n.a
Background and Rationale:	A post market clinical follow up study (PMCF) with Adhese Universal DC is planned to ensure the safety and efficacy of the product. It is a study with two arms. Inlays and onlays for molars and premolars will be luted with Adhese Universal DC or Adhese Universal.
Objective(s):	The null hypothesis is that there is a statistically significant difference between control and test group with respect to postoperative hypersensitivity. The secondary objective of this study is to assess the long-term clinical efficacy of the tested material when compared to the control in terms of marginal quality and retention/fracture rate of the restorations and vitality and fracture rate of treated teeth.
Outcome(s):	The primary endpoint of this RCT is the incidence rate of postoperative hypersensitivity. The secondary outcomes are the vitality and fracture rate of restored teeth and the retention/fracture rate of restorations.
Study design:	Randomised, control clinical trial – Equivalence study
Inclusion / Exclusion criteria:	The participants are aged between 18-65 years. The teeth included in the study show an indication for inlays/ onlays (defective restoration or decay), are vital, with healthy periodontium, and contact with at least one adjacent tooth and with an opposing tooth. Excluded from the study will be pregnant women, participants with known allergies to the used materials and/or local anaesthetics, participants with severe general diseases, participants with bad oral hygiene and high caries activity. Participants who suffer from symptoms of a SARS-CoV2 infection.
Measurements and procedures:	After information and written informed consent the participants will receive a dental treatment in relation to the restorative indication (caries, tooth/restoration fracture, insufficient restoration etc), which means that the inlay/ onlay cavity will be prepared and a digital impression with an intraoral scanner (Trios 3Shape) will be taken. Then, the cavities will be temporarily restored with provisional restorations. The scans and impressions will be sent to the lab where dental technicians will provide the final restorations made of lithium disilicate e.max CAD. In the following appointment the final restorations will be luted and final corrections as well as the finishing and polishing procedures will be done. The baseline recall will take place 7-10 days after the insertion of the restoration. At the baseline recall the study specific parameters will be evaluated according to the FDI Criteria ranging from 1 excellent to 5 clinically not acceptable. The recalls will be performed at 6, 12, 24, 36 and 60 months.

Clinical Study Protocol - Clinical evaluation of a new dual cure universal adhesive (Adhese Universal DC) in the indirect restorative therapy: A randomised, controlled clinical trial

Study Product / Intervention:	Indirect restorations are bonded to the tooth surface by a dental adhesive. Dental adhesives can be light cured or dual cured. The latest generation of adhesives are universal adhesives. Additionally, a composite luting cement is used to fill the gap between tooth and restoration and to bond the restoration to the adhesive layer as well as the restoration. In the test group of the RCT Adhese Universal DC will be used in conjunction with the luting cement Variolink Esthetic. Adhese Universal DC is a new, universal, dual curing adhesive.
Control Intervention (if applicable):	In the control group Adhese Universal will be used in conjunction with the luting cement Variolink Esthetic. Adhese Universal is a universal, light curing adhesive which has been on the market for 6 years and has proven its clinical efficacy and safety.
Number of Participants with Rationale:	80 Teeth: 40 in the study group and 40 in the control group, at maximum two teeth per participant.
Study Duration:	6 years
Study Schedule:	September 2020 December 2026
Investigator(s):	[name], [name], Tel. [REDACTED] E-Mail: [REDACTED] [name], [name], Tel. [REDACTED] E-Mail: [REDACTED] [name], [name], Tel. [REDACTED] E-Mail: [REDACTED] [name], [name], Tel. [REDACTED] E-Mail: [REDACTED] [name], [name], Tel. [REDACTED] E-Mail: [REDACTED]
Study Centre(s):	This RCT is a single centre study.
Statistical Considerations:	Non-parametric test (Mann-Whitney) between control and study group p=0.1 will be applied regarding the clinical parameters evaluated in this study. The sample was calculated using the G*power Software 3.1.9.7.
GCP Statement:	This study will be conducted in compliance with the protocol, the current version of the Declaration of Helsinki, the ICH-GCP or ISO EN 14155 as well as all national legal and regulatory requirements.

ABBREVIATIONS

Provide a list of abbreviations used on the protocol - to be completed

AE	Adverse Event
BASEC	Business Administration System for Ethical Committees, (https://submissions.swissethics.ch/en/)
CA	Competent Authority (e.g. Swissmedic)
CEC	Competent Ethics Committee
ClinO	Ordinance on Clinical Trials in Human Research (in German: KlinV, in French: OClin, in Italian: OSRUM)
eCRF	Electronic Case Report Form
CTCAE	Common terminology criteria for adverse events
DSUR	Development safety update report
GCP	Good Clinical Practice
IB	Investigator's Brochure
Ho	Null hypothesis
H1	Alternative hypothesis
HRA	Federal Act on Research involving Human Beings (in German: HFG, in French: LRH, in Italian: LRUM)
IMP	Investigational Medicinal Product
IIT	Investigator-initiated Trial
ISO	International Organisation for Standardisation
ITT	Intention to treat
MD	Medical Device
MedDO	Medical Device Ordinance (in German: MepV, in French: ODim)
PI	Principal Investigator
SDV	Source Data Verification
SOP	Standard Operating Procedure
SPC	Summary of product characteristics
SUSAR	Suspected Unexpected Serious Adverse Reaction
TMF	Trial Master File

STUDY SCHEDULE

(SPIRIT #13; ICH E6 6.4.2)

Study Periods	Screening	Treatment, Intervention Period		Follow-up					
Visit	1	2	3	4	5	6	7	8	9
Time (hour, day, week)	-60 days	2 hours	2 hours	7-10d	6 mon	12 mon	24 mon	36 mon	60 mon
Patient Information and Informed Consent	x								
Medical History	x								
In- /Exclusion Criteria	x								
Tooth Examination	x								
Pregnancy Test (only in case of uncertainty)	x								
Randomisation			x						
Vitality test	x	x		x	x	x	x	x	x
VAS for tooth sensitivity		x		x	x	x*	x*	x*	x*
Preparation of tooth, impression and cementation of provisional restoration		x							
Try-in and cementation of final restoration			x						
Use of Adhese Universal DC or Adhese Universal			x						
Primary Variables				x	x	x	x	x	x
Secondary Variables				x	x	x	x	x	x
Adverse events			x	x	x	x	x	x	x

x*: only for participants who suffer from any kind of postoperative hypersensitivity

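### Inlay or onlay is known before randomisation but the stated test does not use it; stratifying by it would bring a small gain if restoration type predicts hypersensitivity

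*Combined protocol and SAP*

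**What the plan says.** The synopsis (Background and Rationale) describes one comparison covering all restoration and tooth types: "Inlays and onlays for molars and premolars will be luted with Adhese Universal DC or Adhese Universal". The outcome section adds: "The primary endpoint of this RCT is the incidence rate of postoperative hypersensitivity". The design is given as "Randomised, control clinical trial – Equivalence study", and the sample as "80 Teeth: 40 in the study group and 40 in the control group, at maximum two teeth per participant".

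The analysis is stated once, under Statistical Considerations: "Non-parametric test (Mann-Whitney) between control and study group p=0.1 will be applied regarding the clinical parameters evaluated in this study". No stratum or covariate is named there.

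The study schedule lists "Preparation of tooth, impression and cementation of provisional restoration" at visit 2 and randomisation at visit 3, the visit at which the final restoration is cemented. The synopsis (Measurements and procedures) gives the same order: the cavity is prepared and scanned, the laboratory makes the restoration, and it is luted at the following appointment. Randomisation is a single row in the schedule. The text available, a synopsis and a schedule, does not describe the method, so it neither states nor excludes stratification.

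**The concern.** A factor fixed before allocation cannot be affected by treatment, so adjusting for it is legitimate. If it also predicts the outcome, leaving it out has two consequences. A chance difference between arms in the mix of inlays and onlays carries over into the observed treatment difference, and the standard error is larger than it need be. In an equivalence study with 40 teeth per arm, such an imbalance could hide a real difference as easily as create a false one.

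Timing matters too. An adjustment written down before outcomes are seen by arm is beyond criticism. The same adjustment added after an imbalance has been noticed would look data-driven.

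**Working it through.** **The plan's own figure.** The 40 teeth per group cannot be reproduced, because effect size, power, sidedness and margin are not given; the text says only "The sample was calculated using the G*power Software 3.1.9.7". One assumed set comes close: standardised difference 0.5, one-sided alpha 0.1, power 80% and Mann-Whitney efficiency 0.955 give 39 per group. The same set with two-sided alpha gives 53.

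**Inputs.** From the documents: 80 teeth, 40 per arm, significance level 0.1. Assumed, because the documents give none of them: half the teeth are onlays, allocation is unstratified, incidence is 5% for inlays and 10% to 25% for onlays (centre 20%), and teeth are independent.

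**Step 1, chance imbalance.** The number of onlays in the test arm is X ~ Hypergeometric(80, 40, 40), and the difference between arms is D = 2X − 40.
- SD(D) = 2 × √(40 × ½ × ½ × 40/79) = 2 × √5.063 = 4.5 teeth
- P(|D| ≥ 8) = P(X ≤ 16 or X ≥ 24) = 0.117
- With a 30/70 mix, the probability is 0.087.

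**Steps 2 and 3, shift and precision.** An imbalance of 8 onlays shifts the arm difference by (8/40) × risk gap. The share of variance removed by stratifying is (gap²/4) / [p̄(1 − p̄)], where p̄ is the mean of the two incidences.

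| Onlay incidence (inlay 5%) | Gap | Shift at 8 onlays | p̄ | Variance removed |
|---|---|---|---|---|
| 10% | 5 points | 1 point | 0.075 | 0.9% |
| 15% | 10 points | 2 points | 0.100 | 2.8% |
| 20% | 15 points | 3 points | 0.125 | 5.1% |
| 25% | 20 points | 4 points | 0.150 | 7.8% |
| 5% | 0 | 0 | 0.050 | 0 |

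For the central case:
- The unadjusted variance is 2 × 0.125 × 0.875/40, so the SE is 0.0740.
- The stratified variance is 2 × [(0.05 × 0.95 + 0.20 × 0.80)/2]/40 = 2 × 0.10375/40, so the SE is 0.0720.
- The 90% confidence interval half-width goes from 1.645 × 0.0740 = 12.2 points to 1.645 × 0.0720 = 11.8 points.

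**Step 4, operating characteristics.** These come from simulation with 200,000 trials per scenario and two-sided alpha 0.1. The unadjusted rank test on a binary outcome is set against a stratified Cochran-Mantel-Haenszel test. Power is for a 20-point difference. The last two columns give type I error among trials in which the test arm has an excess of at least 20 percentage points of the higher-risk type, that is, 8 teeth or more.

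| Incidence in the two types | Power, unadjusted | Power, stratified | Type I error after imbalance, unadjusted | Same, stratified |
|---|---|---|---|---|
| 15% / 15% | 67.5% | 67.1% | 9.6% | 10.1% |
| 20% / 10% | 67.6% | 67.7% | 10.9% | 10.2% |
| 25% / 5% | 67.6% | 69.4% | 14.5% | 10.0% |
| 40% / 10% | 58.0% | 63.1% | 17.0% | 9.9% |

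Over all allocations the unadjusted test rejects in 9.9% to 10.1% of null trials, so it keeps its nominal 10% level.

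**Step 5, events available.** At p̄ = 0.125, 80 teeth give about 10 events: 0.05 × 40 = 2 in inlays and 0.20 × 40 = 8 in onlays. Crossing with premolar/molar makes four strata, with 2.5 events each on average.

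**The case against.** The strongest reply is that the plan describes a valid randomised comparison and that adjustment is a preference. Much of this stands. The unadjusted test keeps its level. No passage gives an incidence by restoration type or says that type is prognostic, and the incidences used here are assumptions. In the central case the 3-point shift is about 0.4 of the standard error (3/7.4) and a quarter of the confidence interval half-width (3/12.2). It also needs an imbalance that occurs in about one trial in eight or nine. The clearly inflated conditional error rates appear only at risk gaps of 20 points or more.

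A reader might infer more than the documents support, in three ways.
- **That chance imbalance is bound to remain in the result.** This requires unstratified allocation, and a schedule row would not list strata in any protocol.
- **That precision is certainly lost.** It is lost only if type predicts the outcome.
- **That both factors should define the strata and the randomisation list should be redrawn.** With about 10 events, four strata are too sparse. Every figure above concerns inlay versus onlay, not tooth type. The text shows neither the randomisation method nor the recruitment status.

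The reply does not remove the case for stating a stratified estimate in advance. The factor is a legitimate baseline variable, using it costs very little, and it guards against an imbalance that the stated test ignores.

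**Conclusion.** The point holds as a minor, conditional improvement; it is not a flaw that invalidates the analysis. If restoration type predicts hypersensitivity and allocation is not stratified by it, an imbalance of 8 or more onlays has probability 12% at a 50/50 mix. At 8 onlays the arm difference moves by about 2 to 4 points for risk gaps of 10 to 20 points. The variance is about 1% to 8% larger than it need be for gaps of 5 to 20 points. At 5% versus 20% the power gain is under 1 point. If type is not prognostic, there is nothing to gain.

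All sizes rest on assumed incidences, an assumed mix and independent teeth. Because a participant may contribute two teeth, the real imbalance and standard errors may differ from these.

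**What to change.** Before outcomes are seen by arm, add the following to the analysis plan.

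- State whether randomisation is stratified by restoration type. If it is already stratified, use the strata actually used.
- For hypersensitivity incidence, report a Mantel-Haenszel risk difference with its confidence interval, stratified by inlay/onlay only. An interval also suits an equivalence design better than a p-value does.
- For FDI grades, use a van Elteren (stratified Wilcoxon) test.
- In both, allow for up to two teeth per participant, by a cluster-robust variance or by resampling that respects participants and the way teeth were allocated.
- Keep premolar/molar as a sensitivity analysis, because events are few.

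The cost is analysis-plan wording and slightly more analysis work. If restoration type is not prognostic, power falls by about 0.4 points (67.5% to 67.1% in the simulated case).

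### The synopsis calls the trial an equivalence study but names only a Mann-Whitney test for a difference, with no margin or decision rule, so equivalence cannot be established as written

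*Combined protocol and SAP*

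**What the plan says.** Four synopsis entries bear on this point.

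- **Study design** ends with the label "Equivalence study".
- **Objective(s)**: "The null hypothesis is that there is a statistically significant difference between control and test group with respect to postoperative hypersensitivity".
- **Outcome(s)**: "The primary endpoint of this RCT is the incidence rate of postoperative hypersensitivity".
- **Statistical Considerations**: "Non-parametric test (Mann-Whitney) between control and study group p=0.1 will be applied regarding the clinical parameters evaluated in this study". The entry adds only which sample-size software was used.

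The number of participants is given as "80 Teeth: 40 in the study group and 40 in the control group, at maximum two teeth per participant". The study schedule table also collects a "VAS for tooth sensitivity" and lists "Primary Variables" at six visits, from 7-10 days to 60 months. None of this text gives a margin, a confidence-interval rule, the sidedness of the test, a power, an effect size or an expected incidence.

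**The concern.** A null hypothesis that a difference exists points the right way for an equivalence trial. As worded it has three defects.

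1. It is defined by statistical significance. That is a property of the sample result, not a statement about the true difference, so it is not a testable hypothesis.
2. It has no margin. Without one, equivalence has no meaning that data could confirm or refute.
3. It does not match the named test, whose own null is that the groups do not differ.

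The threshold of 0.1 does not repair this. A difference test at 0.1 is not a pair of one-sided 5% tests against a margin. A rank test can suit the ordinal FDI scores and the VAS, but for an incidence it yields no risk difference to set against a margin.

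At stake is the primary conclusion of a post-market study. The only apparent route from the named test to an equivalence claim is to treat non-significance as proof of equivalence. No sentence states that rule; it is inferred from the label and the test. If used, it would not control the chance of a false claim, and a smaller or noisier trial would meet it more easily.

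**Working it through.** **The plan's own figure.** The 40 teeth per arm cannot be reproduced, because power, effect size, rates, sidedness and margin are not given. Solving backwards for a continuous score, with Mann-Whitney efficiency 0.955:

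d = (z for alpha + z for power) × √(2/40) / √0.955

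- Two-sided 0.1, 80% power: (1.645 + 0.842) × 0.2236 / 0.977 = 0.57 SD.
- Two-sided 0.1, 90% power: 0.67 SD.
- One-sided 0.1, 80% power: 0.49 SD.

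Many input sets give 40, so the sample size implies no particular margin.

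**Inputs for the rest.** From the synopsis: 40 teeth per arm and a threshold of 0.1. Assumed, because the documents give none: all incidences, margins and within-participant correlations. The endpoint is treated as yes/no per tooth, with teeth independent unless stated.

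**One worked table, 10/40 against 5/40.**

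- Pooled proportion 15/80 = 0.1875.
- Tie-corrected variance = 0.1875 × 0.8125 × (2/40) × (80/79) = 0.00771; standard error 0.0878.
- z = 0.125 / 0.0878 = 1.42, two-sided p = 0.155, not significant at 0.1.
- Wald 90% interval: 0.125 ± 1.645 × √(0.25×0.75/40 + 0.125×0.875/40) = 0.125 ± 0.142, or -2 to +27 points. The Newcombe interval agrees to the point.

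The difference test is non-significant, yet the data are compatible with a 27-point excess.

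**Chance of a non-significant result when the arms truly differ.** All pairs of binomial counts were enumerated and the probability of p ≥ 0.1 summed, 40 per arm.

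| True incidences | Two-sided | One-sided |
|---|---|---|
| 5% vs 10% | 76% | 65% |
| 10% vs 20% | 65% | 51% |
| 20% vs 35% | 55% | 41% |
| 10% vs 25% | 44% | 30% |
| 5% vs 20% | 32% | 20% |

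At 10% vs 25%, two-sided, the chance is 65% with 20 per arm, 44% with 40 and 18% with 80, so the smaller trial passes more often. If the test is instead run on a continuous score (simulated normal data, 40 per arm, two-sided), it is non-significant in about 63%, 47% and 31% of trials at true shifts of 0.3, 0.4 and 0.5 SD.

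**What a proper equivalence rule could deliver with 40 per arm.** Power is the chance that the whole 90% interval lies within ± the margin when the true incidences are equal (Newcombe / Wald).

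| Incidence | Margin 10 points | 15 points | 20 points |
|---|---|---|---|
| 5% | 17 / 42% | 64 / 84% | 93 / 97% |
| 10% | 3 / 9% | 38 / 47% | 78 / 80% |
| 20% | 0 / 0% | 8 / 8% | 46 / 46% |

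Part of the Wald advantage is bought with error: at 5% vs 20% and a 15-point margin it declares equivalence falsely in 6.7% of trials.

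Approximate teeth per arm for 80% power: n = (1.645 + 1.282)² × 2p(1-p) / margin². At 10% incidence this is 8.56 × 0.18 / margin², or 155, 69 and 39 for 10, 15 and 20 points.

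**Two teeth per participant.** In the worst case every participant contributes two teeth to the same arm, and the design effect is 1 + ICC.

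- ICC 0.2: 40/1.2 = 33 effective teeth per arm. ICC 0.5: 40/1.5 = 27.
- At 10% incidence, Newcombe power falls from 78% to 61% and 48% (20 points), and from 38% to 21% and 10% (15 points).
- At 10% vs 30% with a 20-point margin, an interval that ignores clustering falsely declares equivalence in 6.8% and 8.8% of simulated trials, against 5.3% with independent teeth.

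**The case against.** The strongest objection is scope. The text available is a synopsis, an abbreviation list and a visit schedule. A sample size was calculated, so inputs existed, and a fuller statistics section may hold a margin or interval rule. This limit stands, and the finding does not extend to text outside those parts. It does not remove the contradiction inside the synopsis: a margin elsewhere would not make the stated null rejectable by the named test.

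Second, the synopsis applies Mann-Whitney to the clinical parameters generally and never says it decides the primary endpoint. It may have been meant for the FDI scores. That is a fair reading, but no other test is named, so the primary endpoint would then have no analysis at all.

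Third, the wording of the null may be a drafting slip, and 0.1 may be a trace of a 90% interval. Both are possible. Neither supplies a margin.

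Fourth, the harm is conditional: nothing says non-significance will be read as equivalence, and every rate, margin and ICC above is assumed. This is accepted. The clustering figures are also a worst case, since an unpaired interval could be conservative if teeth are split between arms.

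Fifth, the risk-difference scale, a single visit and the particular interval method are choices among defensible ones. That is right. What is not optional is a justified margin, a matching decision rule and stated handling of paired teeth, or removal of the equivalence label.

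**Conclusion.** The concern holds and must be fixed. Followed exactly, the synopsis cannot reject its stated null or support equivalence; this is an error in the text and not only missing detail. The logical point depends on no assumed number. Its practical size does: across the assumed incidence pairs, reading non-significance as equivalence would pass trials with true differences of 5 to 15 points 32% to 76% of the time (two-sided). The calculations also show that a correct rule would be demanding. With 40 independent teeth per arm and 10% incidence, only a margin near 20 points reaches about 80% power, and clustering lowers that.

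**What to change.** 1. Restate the hypotheses about true incidences: H0: |p_test - p_control| ≥ delta; H1: |p_test - p_control| < delta. Justify delta from outside this trial's data, and fix and date it before any outcome is compared by group.
2. Make the primary analysis the risk difference at one named visit with a 90% confidence interval, equivalent to two one-sided 5% tests. Declare equivalence only if the whole interval lies within ±delta.
3. State whether a participant's two teeth can be in the same arm. If so, use a cluster-robust or GEE-based interval with a small-sample correction; if they are split between arms, use one that exploits the pairing.
4. Keep Mann-Whitney as supportive for the FDI and VAS scores.
5. Report the power of 40 teeth per arm for the chosen delta, naming the interval method, incidence and ICC assumed.
6. If 80 teeth cannot support any defensible delta, drop the equivalence label and report the risk difference with its interval as estimation.

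The cost is an amendment to the objective and statistics text; restating or relabelling needs no new patients or data. The drawback is that equivalence becomes harder to claim, and a tight margin would need more teeth. Timing matters too. The schedule reads "September 2020 December 2026" while protocol version 03 is dated 10.03.2021, so enrolment may already have begun (the text does not say). The amendment should therefore record when and on what basis the margin was set.

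### The synopsis names only an unpaired Mann-Whitney test for up to two teeth per participant and does not say how the second tooth is allocated, so the true error can lie above or below the planned 10%.

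*Combined protocol and SAP*

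**What the plan says.** The synopsis row Number of Participants with Rationale gives "80 Teeth: 40 in the study group and 40 in the control group, at maximum two teeth per participant". Despite its title, the row gives no number of participants.

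The row Statistical Considerations gives the whole analysis: "Non-parametric test (Mann-Whitney) between control and study group p=0.1 will be applied regarding the clinical parameters evaluated in this study". On sample size it adds only "The sample was calculated using the G*power Software 3.1.9.7". No effect size, power, event rate, margin or within-participant correlation accompanies it.

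Under Outcome(s), "The primary endpoint of this RCT is the incidence rate of postoperative hypersensitivity", without saying whether the incidence is counted per tooth or per participant. The Study Schedule marks randomisation at visit 3 but names no unit. Its VAS row is headed as tooth sensitivity, yet its footnote restricts the VAS from 12 months on: "only for participants who suffer from any kind of postoperative hypersensitivity". Teeth and participants are therefore both used as the unit, and no rule connects them.

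**The concern.** The Mann-Whitney test takes its variance from independent observations. Two teeth in one mouth are unlikely to be independent for this outcome, because the same person reports the pain score for both. Positive correlation is the reasonable expectation, although its size is unknown.

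The consequence depends on how the pair is allocated:

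- **Both teeth in the same arm.** The variance of the group difference is larger than the test assumes. False differences appear too often, and 40 teeth per arm carry less information than 40 independent teeth.
- **One tooth in each arm.** The variance is smaller than assumed. The unpaired test is too conservative and loses power.
- **Teeth randomised one by one, ignoring the participant.** The two effects roughly cancel, and the error stays about nominal.

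The text does not say which case applies, so a reader cannot tell what error rate the stated test would have.

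**Working it through.** **The plan's own figure.** The 80 teeth cannot be reproduced, because only the software is named. Working backwards from 40 independent teeth per arm at a two-sided 0.10 level, the detectable standardised difference at 80% power is (1.645 + 0.842) × √(2/40) = 0.56, or about 0.57 for Mann-Whitney. This shows what 80 teeth could correspond to. It does not show that 80 is wrong.

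**Inputs from the synopsis.** 40 teeth per arm, at most two teeth per participant, and p=0.1, read here as a two-sided 10% level (sidedness is not stated).

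**Assumptions not in the documents.** ρ is the correlation between two teeth of one participant, 0.1 to 0.5. f is the share of teeth that come from two-tooth participants, 0.25 to 1. The number of participants is 80 × (1 − f/2), so 70 at f=0.25 and 40 at f=1.

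**Formulas.**
- Variance factor: 1 + ρf if pairs share an arm, 1 − ρf if pairs are split.
- True two-sided error: 2 × [1 − Φ(1.645/√factor)].
- Effective teeth per arm (same arm only): 40/factor.

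| f | ρ | Same arm: factor, error, effective teeth per arm | Split: factor, error |
|---|---|---|---|
| 0.25 | 0.1 | 1.025, 10.4%, 39 | 0.975, 9.6% |
| 0.5 | 0.3 | 1.15, 12.5%, 35 | 0.85, 7.4% |
| 1 | 0.3 | 1.30, 14.9%, 31 | 0.70, 4.9% |
| 1 | 0.5 | 1.50, 17.9%, 27 | 0.50, 2.0% |

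For the last row: 1.645/√1.5 = 1.343, giving 17.9%; 1.645/√0.5 = 2.326, giving 2.0%; 40/1.5 = 26.7.

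**Simulation of the named test.** Each setting used 100,000 trials of 40 v 40 correlated binary teeth, with incidence 10%, 20% or 30%, ρ from 0 to 0.5 and f of 0.25, 0.5 or 1. The tie-corrected Mann-Whitney test was run at 0.1. With ρ=0 the error was 9.7% to 11.0%, so the test itself is adequate for independent teeth. With ρ of 0.1 to 0.5:

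| Allocation of pairs | Mann-Whitney error, all settings | Mann-Whitney at 20% incidence, f=1, ρ=0.5 | Participant-clustered risk difference, same setting |
|---|---|---|---|
| Same arm | 10.2% to 19.6% | 18.6% | 10.5% |
| Split | 10.7% down to 2.2% | 2.2% | 9.7% |
| Tooth by tooth | 9.8% to 10.9% | 10.0% | 10.1% |

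Over all settings and all three allocations, the clustered risk difference gave 9.6% to 11.4%.

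A separate simulation set the correlation on an underlying normal scale. At 0.5 with f=1 and 20% incidence, it gave 15.3% (same arm) and 5.1% (split). This agrees with the formula: a latent correlation of 0.5 is about 0.29 between binary outcomes at 20% incidence, and factors of 1.29 and 0.71 give 14.8% and 5.1%.

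**Illustrative power.** For 30% v 10%, f=1 and latent correlation 0.5 (tooth-level about 0.25 to 0.34), 60,000 trials gave:

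| Allocation of pairs | Mann-Whitney | Clustered |
|---|---|---|
| Same arm | 71.9% (with inflated error) | 64.5% |
| Split | 77.9% | 85.7% |
| Tooth by tooth | 74.7% | 73.8% |

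**The case against.** **Only part of a protocol is available.** The text consists of a synopsis, an abbreviation list and a visit schedule. A fuller section could give the allocation rule and a clustered analysis. This stands as a limit on scope: the point concerns what the synopsis states. If another section settles the matter, the synopsis still has to agree with it, because at present it names a test that assumes independent teeth.

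**The errors computed are for a test of difference.** The synopsis labels the trial "Randomised, control clinical trial – Equivalence study", and its null hypothesis is that a difference exists. A type I error would then be a false claim of equivalence, which these figures do not measure. That is correct, and the absent margin is a separate issue. It does not rescue the named test, though. An equivalence conclusion also needs the right standard error, and the same correlation distorts it.

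**Tooth-by-tooth randomisation would be harmless.** Counting 40 teeth per group is compatible with it. The error then stays near nominal and clustering costs about one point of power. This stands, but the text does not say that it is the case.

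**The size rests on assumptions.** The ends of the range, 17.9% and 2.0%, require every participant to contribute two teeth and ρ=0.5. At f=0.25 and ρ of 0.1 to 0.2 the same-arm error is only 10.4% to 10.8%. The schedule footnote governs who is assessed from 12 months; it does not prove that two teeth share a score. All of this stands, and it is why the result is given as a range.

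**The clustered test is not exact when events are few.** At 3% to 5% incidence its error ranged from 2.4% to 11.1% in simulation. It can therefore be very conservative if hypersensitivity is rare, but it was not materially anti-conservative.

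**Conclusion.** The concern holds. The synopsis names a test for independent teeth, permits pairs, and leaves the allocation of pairs open. In two of the three plausible allocations the stated test has the wrong error rate: above 10% when pairs share an arm and below 10% when they are split. In the third it is about right. Depending on the number of pairs and the correlation, the departure runs from negligible to nearly double, or to one fifth, of the nominal level. The same-arm case reduces 40 teeth per arm to between 39 and 27 effective teeth.

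These sizes assume positive correlation, a two-sided 10% test of difference, and the stated ranges for ρ and f. The sample size of 40 per arm is not shown to be wrong, because its inputs are not given. This should be fixed; confidence is medium, because the size depends on quantities that the documents do not report.

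**What to change.** 1. **Allocation and unit.** State the unit of randomisation, whether two teeth of one participant receive the same or different adhesives, and whether the primary incidence is per tooth or per participant.
2. **Primary incidence.** Replace the tooth-level Mann-Whitney test with a risk difference per tooth using participant-clustered robust variance, a small-sample correction, and a t reference with participants minus 2 degrees of freedom. Report a two-sided 90% interval to match p=0.1; this interval would also serve an equivalence reading once a margin is set. An exchangeable GEE with corrected robust standard errors is an alternative.
3. **FDI and VAS scores.** Use a clustered rank-sum test in a version that allows both arms within one participant, or an ordinal or linear model with a participant random effect.
4. **Sample size.** Restate it in participants and teeth, with the assumed ρ and f, using the factor 1 + ρf if pairs share an arm or 1 − ρf if they are split.

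The cost is mainly wording, plus a link from each tooth record to its participant, which I assume is feasible. If pairs share an arm, the interval widens and the effective sample shrinks (64.5% power instead of an apparent 71.9% in the illustration). With tooth-by-tooth randomisation about one point of power is lost; with split pairs power rises. The protocol version is dated March 2021 and the schedule starts in September 2020, so enrolment may already have begun. In that case item 1 should record the allocation rule actually used, and item 4 should report the precision achievable with the teeth enrolled.
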